# (Serious) Adverse Events

## Adverse events (AE)

The main criterion for treatment tolerability is the occurrence of toxicities and adverse events. The severity and causality will be classified according to the NCI CTCAE v4.0. The CTCAE v4.0 is available for downloading (http://evs.nci.nih.gov/ftp1/CTCAE/About.html).

An AE is defined as any untoward medical occurrence that occurs from the date of signature of inform consent until 30 days after all trial treatment discontinuation, regardless of whether it is considered related to a medication.

#### Serious Adverse Events (SAE)

A SAE is defined in general as any undesirable medical occurrence/adverse drug experience that, at any dose:

- results in death (any cause, except progression of cancer under study)
- is life-threatening
- requires or prolongs inpatient hospitalization (>24 hours)
- results in persistent or significant disability/incapacity
- constitutes an important medical event
- is a congenital anomaly or birth defect (including neonatal deaths and abortions)
- is a secondary malignancy/second primary malignancy

#### Adverse events of special interest (AESI)

AEs of special interest for this trial are the following:

- **Drug-induced liver injury.** Cases of potential drug-induced liver injury that include an elevated ALT or AST in combination with either an elevated bilirubin or clinical jaundice, as defined by Hy's law.
- **Suspected transmission of an infectious agent by the IMP.** Any organism, virus, or infectious particle (e.g., prion protein transmitting spongiform encephalopathy), pathogenic or non-pathogenic, is considered an infectious agent. A transmission of an infectious agent may be suspected from clinical symptoms or laboratory findings indicating an infection in a patient exposed to a medicinal product. This term applies only when a contamination of the study drug is suspected.

- Adverse events associated with an overdose. An overdose is the accidental or intentional use of a drug in an amount higher than the dose being studied. An overdose or incorrect administration of IMP is not itself an AE, but it may result in an AE.

#### Severity Grade of (serious) adverse event

The (serious) AE severity grade provides a qualitative assessment of the extent or intensity of a specific event, as determined by the investigator or as reported by the patient. *The severity grade does not reflect the clinical seriousness of the event*, only the degree or extent of the affliction or occurrence (e.g. severe nausea, mild seizure), and does not reflect the relationship to trial drug. Severity grade for other adverse events not covered in the toxicity grading scale:

| Grade 1 | Mild- transient or mild discomfort; no limitation in activity; no medical intervention/therapy required  |
|---------|--|
| Grade 2 | Moderate- mild to tolerate limitation in activity; some assistance may be needed; no or minimal medical intervention/therapy required  |
| Grade 3 | Severe- marked limitation in activity, some assistance usually required; medical intervention/therapy required, hospitalization is possible                                    |
| Grade 4 | Life-threatening- extreme limitation in activity, significant assistance required; significant medical intervention/therapy required, hospitalization or hospice care probable |
| Grade 5 | Fatal- the event results in death  |

#### Causality of (serious) adverse event

The investigator must determine the relationship between the administration of trial drug(s) and the occurrence of an AE/SAE following the definitions indicated below:

- Not suspected (unrelated/unlikely): The temporal relationship of the adverse event to trial drug(s) administration makes a causal relationship unlikely or remote, or other medications, therapeutic interventions, or underlying conditions provide a sufficient explanation for the observed event.
- Suspected (possible/probable/definite): The temporal relationship of the adverse event to trial drug(s) administration makes a causal relationship possible, and other medications, therapeutic interventions, or underlying conditions do not provide a sufficient explanation for the observed event.

# 2.3 Analysis populations

**Intention-To-Treat Cohort:** The Intention-To-Treat (ITT) cohort will include all patients enrolled in the trial.

**Efficacy Cohort:** The efficacy cohort will encompass all evaluable patients, i.e., all enrolled patients excluding patients that were found to be ineligible (in retrospective review), patients that have never started the trial treatment and patients that are lost to follow-up before their first response evaluation (by RECIST 1.1).

**Safety Cohort:** The safety cohort will include all enrolled patients that have received at least one dose of trial treatment.

# 3 Primary efficacy analysis of OR

The **primary analysis of OR** will be performed on all the patients included in the **efficacy cohort**. OR rate (ORR) will be estimated as the rate of patients achieving CR or PR over the total number of patients in the efficacy cohort, along with the corresponding 95% exact binomial confidence interval (CI).

#### Formal hypothesis testing

According to the protocol, the trial has been designed to test the null hypothesis Ho: ORR0  $\leq$  0.15 versus the alternative HA: ORRA >0.15 evaluated at 0.35, using a one-sided exact test for proportions, at a one-sided significance level of 0.025 and a power of at least 0.80. The attained alpha of 0.015 and power of 82% will be achieved with a sample size of 41 evaluable patients. The null hypothesis H0 would be rejected and the alternative hypothesis HA accepted if at least 12 patients achieve OR.

Due to trial's premature closure, the target sample size has not been reached and, thus the above formal testing cannot be performed. However, an adhoc hypothesis testing (based again on binomial distribution) will be performed using the available data.

OR analysis will also include:

- A waterfall plot to graphically depict the best percent change in tumor size (sum of target lesions diameter) from the baseline tumor assessment before enrolment.
- A spider plot to graphically depict the percent changes in tumor size (sum of target lesions diameter) from the baseline tumor assessment before enrolment, over time.
- Depending on the number of available responses (i.e., if at least 5), the use of univariate and multivariate logistic regression models will be explored to investigate the effect of the clinicopathological variables of interest (gender, age category, smoking history, ECOG performance status at enrolment, and stage at enrolment) on ORR.

# 4 Additional secondary analyses

In this section, detailed information about the additional analyses that will be performed in the frame of the final efficacy analysis for ALERT-lung trial is presented.

#### 4.1 Patient accrual and baseline characteristics

- Patient accrual by centre and by country will be presented in tabular format.
- In addition, expected vs. observed accrual will be graphically displayed.
- For patients deemed ineligible (patients registered in the online database but eventually not enrolled), a table summarizing the reasons for non-enrolment will be provided.
- Patient & tumor baseline characteristics (categorical variables: ethnicity, gender, smoking history, ECOG performance status at enrolment, tumor stage at enrolment, and continuous variables: age at enrolment) will be presented. Frequencies and corresponding percentages will be presented for categorical variables (if missing cases exist, a separate category named "*Missing*" will be created), while the following descriptive measures will be considered for the continuous variables: n (non-missing sample size), mean, 95% CI for the mean, median, maximum and minimum value.
- Also available information on medical history and prior treatment will be summarised.
- Molecular characteristics at baseline (enrolment): Type of RET fusion and other transcripts; Co-mutations detected with either Next Generation Sequencing (NGS), or Copy Number Variations. Comparisons will also be performed with assessments at subsequent time points (PD) whenever available.

Note: For the efficacy analysis (e.g. subgroup analysis, logistic regression models) age will be categorised according to the observed median.

#### 4.2 Follow-up information and treatment administration

Firstly, a consort flow diagram will be created.

Median follow-up (FU) of the patients along with the respective interquartile range (IQR) and the number (%) of patients that are still alive, will be summarized in a table. Median follow-up time will be estimated based on the method of reverse censoring of OS. A Kaplan-Meier plot will be provided for illustrative reason.

Treatment information will be summarized and presented in a tabular format. More specifically:

- The number of patients that started treatment will be reported. For those patients enrolled, progressed but with physician's and their own agreement continued receiving treatment, information on treatment failure after first progression will be additionally provided.
- The number of patients that did not receive any dose of trial treatment, along with reasons for not doing so will also be presented.
- Number of treatment failures, the 6-month TTF estimate and median TTF time along with the corresponding 95% CIs and the reasons for treatment failure/discontinuation will be presented.
- TTF will be graphically depicted via a Kaplan Meier plot.
- For patients with treatment failure, information for further lines of treatment will also be provided.

## 4.3 Secondary and exploratory efficacy endpoints

#### 4.3.1 Disease control rate

**Clinical efficacy** will be further explored by the estimation of **disease control rate (DCR) in the efficacy cohort**.

- Disease control rate (DCR) at 24 weeks will be presented along with its 95% exact binomial CI.
- The use of univariate and multivariate logistic regression models will be considered (if possible, taking into account the limited number of enrolled patients) to investigate the effect of the clinicopathological variables of interest (gender, age category, smoking history, ECOG performance status at enrolment, and stage at enrolment) on DCR.

#### 4.3.2 Progression-free survival

**PFS** will be evaluated in the **efficacy cohort** by the Kaplan-Meier method. Specifically, the PFS analysis will include:

- The total number (%) of PFS events observed, the 6-month estimate, median and respective 95% CIs.

- Graphical representation of PFS via Kaplan-Meir plots, overall and separately by each clinicopathological variable of interest (if possible due to the limited number of enrolled patients).
- A table with information about the sites of progression.

# 4.3.3 Overall survival

Similar to PFS, **OS** will be evaluated in the **efficacy cohort**. OS analysis will include:

- The total number (%) of OS events observed, the 12-month estimate, median and respective 95% CIs.
- Graphical representation of OS via Kaplan-Meir plots, overall and separately by each clinicopathological variable of interest (if possible due to the limited number of enrolled patients).
- Summary table of the death causes.

# 4.3.4 Sensitivity efficacy analysis

A secondary analysis of all efficacy endpoints evaluated in the **ITT cohort** (if different than the efficacy cohort) will also be performed. Efficacy endpoints to be re-assessed include overall response rate (ORR), disease control rate (DCR) at 24 weeks, progression-free survival (PFS), overall survival (OS).

# 4.3.5 Safety and tolerability

The **safety and the tolerability** of the trial treatment will be evaluated by the **occurrence of AEs** on all patients that have received at least one dose of trial treatment **(safety cohort)**. Classification of severity and causality will be performed according to CTCAE v4.0 and will be presented using tables and bar charts. For each subject, each AE will be analysed according to the worst grade of toxicity observed over the whole treatment period.

Safety and tolerability assessment will include the following:

- Overview of the number of patients who experienced an AE/SAE, as well as the number of patients in the safety cohort who did not experience an event, along with respective percentages.
- Number of AEs/SAEs/AESIs (any cause or treatment-related) and rate of occurrence per month of follow-up.
- Number of patients experiencing a specific number of AEs/SAEs.

- Distribution of AEs/SAEs by grade and CTCAE category. Six columns, one for each grade and one for all (any) grades, will be shown. An additional column indicating which events were SAEs -or started as AEs and became SAEs later on- will be also available. In this column, the frequency of the SAEs and the severity grade will be given. The percentages that will accompany the frequencies will be based on the respective frequency of an event over the total number of patients in the safety cohort. This table will include all AEs/SAEs irrespective of their relation to the trial treatment.
- Analogous table focusing only on the treatment related AEs/SAEs.
- A bar plot illustrating frequencies of AEs/SAEs (only AEs/SAEs with frequency >2% (or any other relevant %) will be presented). A similar plot by CTCAE category will be produced.
- A bar plot illustrating frequencies of treatment related AEs/SAEs.
- Number and corresponding percentages of treatment related AEs/SAEs, leading either to treatment discontinuation or death.
- Maximum severity of AEs/SAEs per patient.
- Number of SAEs by centre.
- For all fatal SAEs, cause of death will be provided.

#### 4.3.6 Subgroup analysis

Further exploratory analyses include description of primary (ORR) and secondary (DCR, PFS, OS) outcomes for patient subgroups of interest, as defined by the following patient or tumour characteristics:

- Smoking status (Current/Former vs Never)
- Gender
- Age group
- ECOG PS
- Stage
- Type of prior treatments

Additional subgroup analysis will be performed by molecular characteristics (at enrolment):

- Type of RET fusion
- Co-mutations detected

Of note, due to the small number of patients, these analyses will be mainly of exploratory nature. Depending on data, Fisher's exact test will be used for comparing ORR, DCR and log-rank test for comparing PFS, OS between different subgroups of patients.

# 5 Technical details

Data will be primarily analysed using the SAS software package (version 9.4), while the R statistical software will be also used for specific analyses and plots.

All final analysis and reviews will be performed according to the Standard Operating Procedures (SOPs) of the Frontier-Science Foundation Hellas (FSFH) statistical team. A second statistician, the reviewing statistician, will independently reproduce all analyses and summary statistics. The reviewing statistician will have an overview of the entire analysis and will explicitly check the code producing tables and figures, as well as any other pieces of code as desired.

#### 5.1 Data Retrieval Information

On February 8, 2021, ETOP announced the premature closure of the ALERT-lung trial (ETOP 12-17 ALERT-lung Trial Closure Guidance Letter). **Trial will be terminated by March 31, 2021**. **Follow-up and safety information will be updated until March 31. All outstanding data and query replies will be submitted by 28 February 2021. Final database lock and trial closure date will be on 31 March 2021**.

#### 5.2 Missing Data

#### **Baseline characteristics**

For categorical baseline characteristics if missing cases exist, a separate category named 'Missing' will be created. As far as continuous values, missing cases will not be replaced by any statistics calculated over non-missing data.

#### Dates

If the day of the month is missing for any date used in the analysis, the 15th of the month will be used to replace the missing date unless the calculation results in a negative time duration (eg, onset date cannot be prior to day one). In this case, the date resulting in one day of duration will be used. If the day of the month and the month are missing for any date used in a calculation, January 1 will be used to replace the missing date. Missing dates for adverse events will be imputed based on the similar principle.

#### Incomplete tumor assessment information

In patients who have no on-study assessments:

- If death is recorded prior to the first planned tumor assessment, the death date will be considered as the date of the PFS event.
- If clinical progression is recorded prior to the first planned tumor assessment, the date of the reported clinical progression will be considered as the date of the PFS event.
- In any other case, the patient will be censored at the date of enrolment plus 1 day.

#### 5.3 Reporting conventions

Regarding the estimates presented in the report, the following rules will be adopted:

- P-values  $\geq 0.001$  will be reported with three decimal places
- P-values >0.010 will be reported with two significant decimal digits
- P-values less than 0.001 will be reported as '<0.001'
- Means, medians, 95% confidence intervals (CIs), quantiles, and any other statistics, will be reported with one decimal digit
- Hazard ratios (HRs) and their 95% CIs will be reported with two decimals
- Estimated parameters, not on the same scale as raw observations (e.g., regression coefficients) will be reported with three significant figures

#### 5.4 Multiple recordings of an event for the same patient

There are some cases where a patient may experience the same event (AE/SAE) more than one time. In such cases, the event will be count only once (with the highest grade) for the calculation of the total number of events.

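### SAP 5.4 counts a recurring AE/SAE once in the event total, so the event count and monthly rate in 4.3.5 fall below the number of episodes whenever an event recurs

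*SAP*

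**What the plan says.** Section 5.4 is headed "Multiple recordings of an event for the same patient". Its text describes the situation in which "a patient may experience the same event (AE/SAE) more than one time" and rules that "the event will be count only once (with the highest grade) for the calculation of the total number of events".

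Section 4.3.5 lists eleven safety outputs for the safety cohort. Three features matter here:

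- **Worst grade.** The introduction states: "For each subject, each AE will be analysed according to the worst grade of toxicity observed over the whole treatment period".
- **Patient-based percentages.** In the table by grade and CTCAE category, percentages are "based on the respective frequency of an event over the total number of patients in the safety cohort".
- **Event-based outputs.** One item is "Number of AEs/SAEs/AESIs (any cause or treatment-related) and rate of occurrence per month of follow-up". Another is "Number of patients experiencing a specific number of AEs/SAEs". A further item tabulates SAEs by centre.

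Nothing in the SAP limits the once-only rule to the patient-based tables, and nothing defines a separate episode count for the event totals or the monthly rate.

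**The concern.** The heading of 5.4 suggests duplicate records of one event, for which counting once is right. The text goes further and covers a patient who has the event again. It also names the total number of events as the quantity to which the rule applies, rather than the number of patients with an event. True recurrences are therefore merged along with duplicates.

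For the monthly rate this leaves numerator and denominator out of step. Repeats drop out of the numerator, but nothing says that follow-up stops at the first occurrence, so all months stay in the denominator. The result is neither an episode rate nor a first-event rate.

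Safety and tolerability is a secondary objective (Section 1.1). The trial is single-arm, so readers will take these absolute figures at face value, and they will read a number of AEs and a rate per month as episodes. Any error from this rule can only make the count smaller.

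**Working it through.** The SAP states no AE count or rate, so there is no planned figure to reproduce. The check has two parts.

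**1. Which outputs the rule reaches**

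| Output in 4.3.5 | Unit implied | Effect of counting once |
|---|---|---|
| Grade and category tables, maximum severity | Patient | Appropriate |
| Number of AEs/SAEs/AESIs and monthly rate | Event | Becomes distinct patient-event pairs |
| Patients by number of events; SAEs by centre | Event | Same change, by inference, since no other rule is given |

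The event count matches the wording of 5.4 closely. Section 5.4 does not name the rate, but a rate of occurrence listed beside that count has no other numerator in the SAP. Section 5.4 also names only AEs and SAEs; AESIs are covered because they are themselves AEs.

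**2. Size of the shortfall**

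Inputs, all assumed because the SAP gives none:

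- r = share of patient-event pairs that recur
- m = episodes in each recurring pair

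Let D be the number of distinct patient-event pairs (what 5.4 counts), E the number of episodes, and T the months of follow-up.

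- Mean episodes per pair: k = 1 + r(m − 1)
- Episodes: E = D × k
- Reported over episode-based rate: (D/T) / (E/T) = 1/k, because T is the same in both
- Understatement: 1 − 1/k

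| r | m | k | Reported / episode figure (1/k) | Understatement |
|---|---|---|---|---|
| 0 | any | 1.0 | 1.00 | 0% |
| 0.1 | 2 | 1.1 | 0.909 | 9.1% |
| 0.2 | 2 | 1.2 | 0.833 | 16.7% |
| 0.3 | 2 | 1.3 | 0.769 | 23.1% |
| 0.3 | 3 | 1.6 | 0.625 | 37.5% |
| 0.5 | 2 | 1.5 | 0.667 | 33.3% |
| 0.5 | 3 | 2.0 | 0.500 | 50.0% |

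*Count example.* Take ten patient-event pairs, three of them with two episodes. Episodes: 7 × 1 + 3 × 2 = 13. Reported under 5.4: 10. Shortfall: 3/13 = 23.1%.

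*Rate example.* Take 100 pairs, 120 episodes and 200 patient-months. Under 5.4: 100/200 = 0.50 per month. By episodes: 120/200 = 0.60 per month.

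The formula applies to the total count and the rate. It does not quantify the effect on the events-per-patient table or on SAEs by centre, which depends on how recurrences are spread over patients and centres.

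**The case against.** The strongest defence is that the rule is disclosed and consistent. Section 5.4 says how events are counted, and the worst-grade sentence in 4.3.5 points the same way. Together they could be read as making the patient-event pair the unit throughout. Counting once at the highest grade is a familiar convention in descriptive safety reporting, and the SAP never promises episode counts, so the figures are low only against a quantity the SAP did not define. It can be added that 5.4 does not mention the monthly rate, that its heading leaves room for a narrower intent, that the size is unknown and may be zero, and that the outputs are descriptive in a single-arm trial closed early.

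Much of this stands. The rate is reached by inference, the magnitudes are illustrations, and the main tolerability tables are unaffected: no patient's worst grade is lost.

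It does not remove the point. The worst-grade sentence selects a grade; it does not turn a once-only numerator into a number of events or a rate per month. If 5.4 was meant only for duplicate records or incidence tables, its text says something else and still needs correcting. Section 5.4 itself anticipates that some patients will have the same event again. Having no control arm also means that no comparison group carries the same undercount, so the absolute figures are what the reader takes away.

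**Conclusion.** The concern holds. Under Section 5.4 as written, the number of AEs/SAEs/AESIs and the monthly rate in 4.3.5 are counts of distinct patient-event pairs, presented as events and a rate of occurrence. They equal the episode figures if no event recurs in a patient and are below them by 1 − 1/k otherwise. Over the assumed values above, that is 0% to 50%; the SAP does not allow a narrower statement.

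The reach is limited. One of the eleven outputs is affected directly and up to two more by inference. All are descriptive, and neither the response analysis nor any decision depends on them. The conclusion rests on reading the event total in 5.4 as the count planned in 4.3.5, the only reading for which the SAP supplies a rule. It should be corrected, but it does not threaten the trial's main conclusions.

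**What to change.** Reword Section 5.4 in two parts.

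1. **Patient-level outputs.** Keep the once-only, highest-grade rule for tables of number and percentage of patients and for worst grade.
2. **Event-level outputs.** For the number of events, the monthly rate, events per patient and SAEs by centre, count each distinct episode. Treat records of one continuing event as one episode at its highest grade. This includes a grade change, or the case 4.3.5 recognises of events that "started as AEs and became SAEs later on", provided there was no resolution in between. Treat an onset after a recorded resolution as a new episode.

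If the data do not separate episodes, keep the present rule, label these outputs as distinct event types per patient, and do not present the monthly figure as an event rate.

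The cost is SAP wording plus some programming for episode counting. The SAP does not show whether the records distinguish episodes. With outstanding data due by 28 February 2021 and database lock on 31 March 2021 (Section 5.1), missing detail could not readily be collected, so the change may reduce to relabelling. Where episodes can be counted, the reported count and rate rise by the factor k: unchanged at k = 1, 1.3 times at k = 1.3 and doubled at k = 2, all assumed values.
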